#### 1.1.3.5 Population Pharmacokinetic and Pharmacodynamic (PKPD) Modeling

A population pharmacokinetic model of lurbinectedin was developed by pooling data from all studies (including drug combination studies) and it is regularly updated.

A population pharmacokinetic three-compartment model with linear elimination and linear distribution adequately fits the PK data. The model estimated a mean (standard deviation [SDev]) CL of 12.3 (7.0) L/h, a half-life (HL) of 47.2 (31.5) hours and a wide volume of distribution at steady state (Vss) of 436 (250) L. All these PK parameters showed high variability (coefficient of variation [CV] about 50%) among patients. The lurbinectedin PK showed linearity among the dose range explored (0.5-4.5 mg/m^2).

Baseline covariates affecting lurbinectedin CL are albumin, alpha 1-acid glycoprotein, BSA, the presence of strong (voriconazole) or moderate (aprepitant or fluconazole)

CYP3A4 inhibitors, and cardiac function measured by left ventricular ejection fraction (LVEF). The use of strong (voriconazole) or moderate (fluconazole or aprepitant) CYP3A4 inhibitors reduced lurtinectedin CL by approximately 40% and 20%, respectively. Therefore, the use of CYP3A4 inhibitors should be carefully monitored or avoided, whenever possible.

Renal elimination of lurtinectedin was minor in the FiH trial. In addition, the population PK model did not establish any relationship between lurtinectedin CL and CLcr or creatinine levels. Age and race were found to have no effect over lurtinectedin PK, although the number of elderly patients (>75 years) and non-Caucasian patients was small.

Lurtinectedin-induced neutropenia and thrombocytopenia population PKPD models showed that baseline ANC and platelet count are by far the covariates with the greatest effect on the incidence of neutropenia and thrombocytopenia. With a baseline absolute neutrophil count (ANC) value of  $2.0 \times 10^9/L$  (currently the lower limit of ANC for inclusion is  $1.5 \times 10^9/L$ ), and a platelet count of  $135 \times 10^9$  (currently the lower limit of platelet count for inclusion is  $100 \times 10^9/L$ ), the incidence of grade 3/4 neutropenia and thrombocytopenia were estimated to be around 69% and 13%, respectively, in the first cycle. Simulations performed at  $3.2 \text{ mg/m}^2$  showed a lower neutropenia and thrombocytopenia incidence compared to the previous RD of  $7.0 \text{ mg FD}$ . The results of the simulation also showed that BSA-dosing reduced the variability caused by BSA compared to  $5.7 \text{ mg FD}$ . The presence of ascites or the use of CYP3A4 inhibitors would increase the incidence of neutropenia, while the use of G-CSF would decrease it markedly. Additionally, breast cancer patients showed less risk of developing thrombocytopenia, while the use of strong CYP3A4 inhibitors, ascites or pancreatic cancer increased this risk. The population PK model of lurtinectedin showed that CL increases with BSA, and the population PKPD models for neutropenia and thrombocytopenia showed myelosuppression would be decreased by BSA dosing. Therefore, the use of a BSA-dosing strategy for lurtinectedin has been resumed in ongoing and planned trials.

## **1.2 OVERALL STUDY RATIONALE**

Lurtinectedin is extensively metabolized by the cytochrome P450 enzymes, primarily CYP3A4. Thus, potent inducers or inhibitors of this enzyme may alter the plasma concentrations of lurtinectedin. This study is designed to examine the PK and safety of lurtinectedin when co-administered with itraconazole, a strong CYP3A4 inhibitor, in comparison with lurtinectedin alone. The results of this study may be used to support future clinical studies in patients and prescribing information in future labeling.

## **1.3 PHARMACOGENETIC SUB-STUDY RATIONALE**

Germline genetic variants may influence exposure and toxicity (i.e. disposition, metabolism and safety) to lurtinectedin. In order to explore the potential impact of genetic factors that may account for inter individual variability in the main PK parameters, blood sample for germline DNA extraction will be collected and stored for future pharmacogenetic (PGt) analysis. One blood sample obtained at any time during the study, but preferably just before infusion start along with PK sample #1 on Day 1 of Cycle will be obtained.

## 2. STUDY OBJECTIVES

### 2.1 PRIMARY OBJECTIVE

- To assess the effect of itraconazole on lurbinectedin total plasma exposure in patients with advanced solid tumors.

### 2.2 SECONDARY OBJECTIVES

- To assess the effect of itraconazole on lurbinectedin unbound plasma exposure.
- To assess the effect of itraconazole on lurbinectedin major metabolites (i.e., M1 and M4).
- To assess the effect of itraconazole on the safety profile of lurbinectedin.
- To collect and store a blood sample for germline DNA extraction for future pharmacogenetic (PGt) analysis of variations on genes that may influence exposure and response (i.e., disposition, metabolism and safety) to lurbinectedin.

## 3. OVERALL STUDY DESIGN

### 3.1 STUDY DESIGN

This is a prospective, open-label, two-way crossover, phase Ib drug-drug interaction study in patients with advanced solid tumors.

The study will include a pre-treatment (screening) phase followed by a treatment phase consisting of two lurbinectedin cycles, one cycle in combination with itraconazole and one cycle of lurbinectedin as single agent (in different order depending on the study sequence), and one additional third cycle of lurbinectedin as a single agent for patients who meet the continuation criteria and obtain a clinical benefit after the first two cycles, and then follow-up of adverse events if any.

Patients who meet the continuation criteria and obtain a clinical benefit after the first two cycles according to the Investigator's criteria will have the opportunity to continue treatment under a Compassionate Use Agreement after the completion of the optional third study cycle.

Patients will be treated as outpatients. At the discretion of the Investigator, patients may be admitted to the study center on Day -1 or Day 1 and monitored, at least, until completion of the Day 1 PK blood sample collections.

Patients will receive a maximum of three cycles: two consecutive cycles of lurbinectedin, one cycle with and one cycle without itraconazole co-administration (in different order depending on the study Sequence 1 or Sequence 2 of treatment), followed by a third cycle with lurbinectedin alone (this last optional for patients with clinical benefit). Lurbinectedin will be administered as a 1-hour (-5/+20 min) i.v. infusion q3wk via a central or peripheral vein.

[figure not shown]
In the co-administration cycles, itraconazole will be administered orally once daily in the morning after breakfast during 12 consecutive days, self-administered at home from Day -4 (i.e., four days before lurbinectedin infusion) until Day 8 (i.e., seven days after lurbinectedin infusion), and supplied at the study center on Day 1, following

recommendations at the Summary of Product Characteristics (SmPC). On Day 1 (i.e., the day of lorbinecetin infusion), itraconazole will be given immediately prior to starting the lorbinecetin infusion. In fact, itraconazole should be administered after obtaining the itraconazole pharmacokinetic (PK) sample #1 and before the start of lorbinecetin infusion (-15 min to -1 min).

In case of lorbinecetin delay ( $\leq 2$  days), itraconazole could be administered during a maximum of 14 days.

This study will consist of two parts (Figure 2): Part A and B. The dose of lorbinecetin when given in combination with itraconazole for the initial three patients in Part A will be  $0.8 \text{ mg/m}^2$ , and in Part B is susceptible to be adjusted properly if deemed necessary based on exposure and safety experience in Part A. The dose of lorbinecetin during Parts A and B will be  $3.2 \text{ mg/m}^2$  for all patients when administered without itraconazole. If toxicity occurs, the appropriate intra-patient dose level (DL) reductions will be implemented in the subsequent cycle. This DL reduction will be according to [Table 8](#).

**Figure 2.** Study design.

\* Planned dose in Part B is susceptible to be adjusted properly if deemed necessary based on exposure and safety experience in Part A.

ITZ, itraconazole; LRB, lorbinecetin; TR, test-reference; R; randomized; RT, reference-test.

In Part A, three patients will be enrolled to Sequence 1 (TR: Test-Reference) and will receive itraconazole with lorbinecetin in Cycle 1 followed by two consecutive cycles of lorbinecetin alone (the last cycle being optional for patients with clinical benefit according to the Investigator's criteria).

Enrollment for Part A will be sequential. Once the first patient enrolled has completed Cycle 1 and Cycle 2, the second and the third patients could be enrolled simultaneously, after the evaluation of lorbinecetin total PK parameters, and if no unacceptable or life-threatening toxicities have occurred for this first patient. However, if toxicity occurs, the appropriate dose reductions will be implemented with the second and third patients based on the PK and safety information of first patient.

The dose of lorbinecetin when given in combination with itraconazole for the initial three patients in Part A will be  $0.8 \text{ mg/m}^2$ . However, if lorbinecetin exposure in the first patient of Part A does not allow an adequate PK assessment, the lorbinecetin dose of the following patients may be increased accordingly.

Upon exposure and safety assessments in Part A, the dose of lorbinecetin to be co-administered with itraconazole in Part B can be readjusted accordingly. This decision will be made by the Sponsor and study Investigators.

Therefore, the planned dose of lorbinecetin, when given with itraconazole for the remaining eight patients in Part B will be based on the acceptability of the PK and safety results from the first three patients in Part A. If the initial three patients do not experience adverse events (AEs) which might require a dose reduction, the dose of lorbinecetin may still be adjusted (based on the assumption of dose-proportional pharmacokinetics) to produce plasma lorbinecetin AUC values that are comparable to those when lorbinecetin is given in the absence of itraconazole. However, if toxicity occurs in the initial three patients in Part A, the appropriate dose-reduction of lorbinecetin will be implemented in Part B accordingly.

If the safety and PK data obtained from the three patients in Part A is deemed acceptable as defined in the protocol, Part B of this study will begin enrollment. Therefore, once Part A is completed, patients in Part B will be enrolled based on the review of the safety following completion of the first cycle of the previous patient(s), and will be randomized in a 1:1 ratio to Sequence 1 (as used in Part A) or Sequence 2 (RT: Reference-Test; lorbinecetin + itraconazole in Cycle 2).

In Part A, all patients will receive itraconazole plus lorbinecetin in Cycle 1 and lorbinecetin alone in Cycles 2 and 3 (this last cycle being optional).

In Part B, patients will be randomly assigned to the corresponding sequences:

- Sequence 1 (TR) (same used in Part A):
  - Cycle 1: Itraconazole + lorbinecetin
  - Cycle 2: Lorbinecetin alone
  - Cycle 3: Lorbinecetin alone (optional)
- Sequence 2 (RT):
  - Cycle 1: Lorbinecetin alone
  - Cycle 2: Itraconazole + lorbinecetin
  - Cycle 3: Lorbinecetin alone (optional)

Lorbinecetin will be administered to 11 evaluable patients and for a maximum of three cycles, while considered to be on the patient's best interest or until PD, unacceptable toxicity, intercurrent illness of sufficient magnitude to preclude safe continuation of the study, patient's refusal and/or non-compliance with study requirements, a protocol deviation with an effect on the risk/benefit ratio of the clinical study, more than two lorbinecetin dose reduction due to AEs related to lorbinecetin (unless clear clinical benefit has been documented and always with the Sponsor's agreement) or any other reason at the physician's judgment that precludes lorbinecetin continuation.

If the patient meets the continuation criteria and shows a clear clinical benefit after the first two cycles, treatment with lorbinecetin may continue outside this study under a Compassionate Use Agreement at the same dose based on Investigator's decision and upon agreement with the Sponsor. Then, the treating center must request authorization to the relevant Health Authorities and notify the Sponsor in due time. In order to avoid a treatment discontinuation, during the Compassionate Use Agreement authorization an additional third cycle with lorbinecetin is allowed.

All adverse events (AEs) will be graded according to the National Cancer Institute Common Terminology Criteria for Adverse Events (NCI-CTCAE) v.5. Treatment delays, dose reduction requirements and reasons for treatment discontinuation will be monitored throughout the study. The safety profile of patients will be monitored

throughout the treatment and up to 31 days ( $\pm 10$  days) after the last lurbinectedin infusion (end of treatment, EOT), until the patient starts a new antitumor therapy or until the date of death, whichever occurs first. Any treatment-emergent AEs will be followed until recovery to at least grade 1 or stabilization of symptoms or until the start of a new antitumor therapy, until the continuation of treatment outside this study under a Compassionate Use Agreement or death, whichever occurs first. After treatment discontinuation, patients will be followed until resolution or stabilization of all toxicities, if any.

Patients will be evaluated at scheduled visits on three study periods: pre-treatment (screening), treatment (one cycle of lurbinectedin in combination with itraconazole and two as a single agent and the third cycle optional) and follow-up of adverse events if any (see Section [Schedule of Assessments and Procedures](#)).

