### **Lurbinectedin**

Lurbinectedin will be administered as a 1-hour (-5/+20 min) i.v. infusion on Day 1 q3wk, [REDACTED]

Patients will receive a maximum of three cycles: two consecutive cycles of lurbinectedin, one cycle with and one cycle without itraconazole co-administration (in different order depending on the Sequence 1 or Sequence 2 of treatment), followed by a third cycle with lurbinectedin alone (this last cycle optional for patients with clinical benefit).

The dose of lurbinectedin when given in combination with itraconazole for the initial three patients in Part A will be 0.8 mg/m^2. Lurbinectedin dose in Part B will be based on the acceptability of the PK and safety results from the first three patients in Part A.

In cycles with lurbinectedin as single agent, lurbinectedin will be administered at 3.2 mg/m^2.

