### 9.2 SAMPLE SIZE

A block randomization (1:1 ratio) will be performed only in Part B. At least 11 patients (three patients in Part A followed by eight patients in Part B) are expected to complete all study procedures, including the collection of sufficient and interpretable PK assessments. Although at least 11 patients will be enrolled in this study; it is estimated that complete data from eight patients will be sufficient to estimate the drug-drug interaction of itraconazole on the PK of lubrinezdin. In case of patient replacement, a new patient number will be provided and he/she will be assigned to the same sequence as the patient being replaced.

This study was designed to assess the potential effects of itraconazole on the PK of lubrinezdin in patients with advanced malignancies. The 90% CI will be used to help with the interpretation of the results. A sample size of eight patients was based on feasibility and clinical considerations. Based on previous studies, the intra-subject coefficient of variation (CV) of lubrinezdin PK parameters is estimated to be more than 30%. The precision (half-width) of the 90% CI for [(lubrinezdin + itraconazole) / lubrinezdin alone] comparison on the log-scale will extend 0.389 from the observed differences in means, assuming that the intra-subject CV around 40%. This half-width corresponds to a 90% CI in the range of 70% and 147% assuming the ratio of the means equal to unity for each PK parameter. This 90% CI will be used to help with the interpretation of the results.

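### Part B enrolment is released on Cycle 1 safety, which in Sequence 2 is lurbinectedin alone, so the first review at a possibly changed combination dose has a 50% chance of holding no combination data

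*Protocol*

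**What the plan says.** Three places carry the same release rule: Protocol 3.1, the protocol synopsis (Study Design) and SAP section 2. Once Part A is complete, "patients in Part B will be enrolled based on the review of the safety following completion of the first cycle of the previous patient(s"). Part B patients "will be randomized in a 1:1 ratio to Sequence 1 (as used in Part A) or Sequence 2". For Sequence 2 the same section lists "Cycle 1: Lorbinecetin alone" and then "Cycle 2: Itraconazole + lorbinecetin".

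The sample is "three patients in Part A followed by eight patients in Part B" (Protocol 9.2). The co-administration dose in Part A starts at 0.8 mg/m² (Protocol 7.2). It is not fixed for Part B: even without dose-limiting events in Part A, "the dose of lorbinecetin may still be adjusted (based on the assumption of dose-proportional pharmacokinetics") so that exposure is comparable with that of lurbinectedin given alone. If toxicity occurs in Part A, the Part B dose is to be reduced.

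Part A has its own stagger: "Once the first patient enrolled has completed Cycle 1 and Cycle 2, the second and the third patients could be enrolled simultaneously", after evaluation of that first patient's PK parameters and if there has been no unacceptable or life-threatening toxicity.

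On other oversight, Protocol 6.2 bars treatment before the sponsor agrees to registration. Protocol 8.6 describes ongoing review by the investigators and the sponsor's study team, without a data safety monitoring board.

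**The concern.** A stagger is useful if the data reviewed bear on the risk the next patient will face. In Part B the uncertain element is lurbinectedin plus itraconazole, especially if the co-administration dose has been re-set after Part A. The trigger names the first cycle, not the co-administration cycle. The two coincide in Sequence 1 but not in Sequence 2, where the first cycle is single-agent lurbinectedin at 3.2 mg/m², the regimen already given to 335 patients in one phase II study (Protocol Table 3).

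Followed to the letter, the rule can clear a Sequence 1 patient to start the combination at a changed dose when the only completed Part B cycle contained no itraconazole. Nothing in Protocol 3.1, 6.2, 7.4 or 8.6, or in SAP section 2, makes release depend on a Sequence 2 patient's Cycle 2.

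**Working it through.** The plan gives no figure for this rule, so there is nothing to reproduce. The inputs are eight Part B patients, 1:1 block randomisation (Protocol 9.2) and 21-day cycles. The block size of the main list is not stated, so sizes 2, 4 and 8 are assumed. Replacement patients are ignored.

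**1. First review.** It rests on patient 1's Cycle 1. P(patient 1 in Sequence 2) = 4/8 = 50% for every block size.

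**2. Sequence 2 followed by Sequence 1.** This is the opening in which patient 2 starts the combination early. P = P(first is Sequence 2) × P(second is Sequence 1, given that).

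| Assumed block size | Calculation | Probability |
|---|---|---|
| 2 | 0.5 × 1 | 50% |
| 4 | 0.5 × 2/3 | 33% |
| 8 | 0.5 × 4/7 | 29% |

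**3. Timing of that opening.** Count days from patient 1's first infusion, with no delays and one patient enrolled at a time.
- Day 21: patient 1's Cycle 1 is complete and reviewed, patient 2 can be released, and patient 1 receives the first combination infusion.
- Day 25 at the earliest: patient 2's combination infusion, if patient 2 is already screened and itraconazole (from Day -4, Protocol 7.2) starts only on release.
- About day 31: patient 1's myelosuppression nadir on the combination, taking the middle of the second week (Protocol 1.1) as about 10 days after infusion.
- Day 42: patient 1's combination cycle is complete.

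So patient 2 can be infused before patient 1's nadir and about 42 − 25 = 17 days before patient 1's combination cycle ends. Longer screening narrows the overlap, but the rule does not require any gap.

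**4. Other openings.** If patient 2 is also in Sequence 2, that patient's combination infusion falls at day 21 + 21 = 42, when patient 1's combination cycle has ended. If patients 1 to 3 are Sequence 2, 2, 1, patient 3 is released at day 42 or later, again after that cycle. If patient 1 is in Sequence 1, the first review does contain combination data. On these assumptions at most one patient is exposed to the gap.

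**5. All seven reviews that release patients 2 to 8.**
- If each review covers only the latest patient's first cycle, the expected number without combination data is 7 × 0.5 = 3.5 (3 or 4 in any given list).
- If each review pools the first cycles of all earlier Part B patients, a review is empty only when every patient so far is in Sequence 2. The expected number is 0.5 for block size 2; 0.5 + 1/6 = 0.67 for block size 4; and 0.5 + 3/14 + 1/14 + 1/70 = 0.80 for block size 8. Divided by 7, that is 7%, 10% and 11%.

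The first review is unaffected by this choice: its 50% holds under both readings.

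**The case against.** The strongest reply is that the gap is small and conditional.

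- **The dose may not change.** Protocol Table 8 lists 0.8 mg/m² as the co-administration starting dose for both parts. If Part B uses a dose given in Part A, the Part A patients already supply combination data at it. This stands, and it limits the point to a changed dose.
- **Other controls exist.** A reader might infer that the first-cycle review is the sole check on enrolment. The documents do not support that. The sponsor must agree to each registration (Protocol 6.2), and the approval form records each patient's combination dose (SAP Listing 13.3). A dose change is decided by the sponsor and investigators and communicated to the ethics committee (SAP section 2). Serious events are reported within 24 hours (Protocol 8.5.2), and safety is reviewed continuously (Protocol 8.6). What remains is that none of these requires data from a Sequence 2 patient's Cycle 2 before release.
- **Half of all reviews may not be empty.** That figure needs the reading in which only the latest patient is reviewed. The plural option in the wording allows cumulative review, which brings empty reviews down to about 7–11%.
- **A higher dose in mg/m² is not a higher exposure.** A reader might project how far the Part B dose could exceed 0.8 mg/m² and treat that multiple as the added risk. The adjustment aims at an AUC comparable with lurbinectedin alone and would rest on Part A data that are not yet available, so such a multiple does not measure risk.
- **The contrast with Part A is limited.** The two-cycle wait there applies to one patient and is tied to PK evaluation; the next two may then enrol together.

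**Conclusion.** The mismatch is real and identical in all three places: the release rule refers to the first cycle, and in Sequence 2 that cycle contains no itraconazole. The first Part B review has a 50% chance of holding no combination data, whatever the block size.

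The consequence is narrow. It arises only if the Part B co-administration dose differs from Part A and the opening is Sequence 2 then Sequence 1, with probability 50%, 33% or 29% for assumed block sizes 2, 4 or 8. It then affects at most one patient, given one-at-a-time enrolment, 21-day cycles and no delays. Enrolling several patients together, or a delay to a Sequence 2 patient's Cycle 2, would widen it. The documents do not support a claim that half of Part B is enrolled without relevant safety information, or that no other safeguard operates. They do support the claim that the written rule can release a patient to a changed combination dose before anyone has completed a cycle at it.

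**What to change.** Reconcile Protocol 3.1, the synopsis and SAP section 2 with the sequence definitions. The amended text should state three things:

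1. For the first patient(s) treated at a Part B co-administration dose that differs from Part A, the release review covers the completed co-administration cycle: Cycle 1 in Sequence 1, Cycle 2 in Sequence 2.
2. Whether each review is cumulative over all earlier Part B patients or covers only the latest.
3. If a Sequence 2 patient leaves before Cycle 2, the review passes to the next patient who completes a co-administration cycle. Without this, the trigger might never be met.

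The chance that the first review at a changed dose holds no combination data then falls from 50% to 0. No dose, sample size or analysis changes.

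The cost is a short amendment in three places and a wait of about 21 days if the first patient at the changed dose is in Sequence 2, plus any delay Protocol 7.4 permits (up to 14 days for the itraconazole start and up to 2 more for the infusion). A patient who leaves before Cycle 2 would lengthen the wait, so no firm maximum can be given. Planned enrolment is about 18 months (Protocol 5.1).
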